6.3.3 Efficacy Analysis

The primary endpoint is:

Overall Clinical Success in number and size of lesions or change in organ functionality at 48 weeks

The secondary efficacy endpoints are:

- Overall Clinical Success in number and size of lesions or change in organ functionality at 12 weeks
- CGI scores at 12 and 48 weeks
- Quality of life scores at 12 and 48 weeks

Overall clinical success is defined as 50% of subjects with visible or other measureable lesions achieving at least a 50% improvement in lesion number/size or functionality impact from baseline. Visible lesions are defined as lesions which can be imaged and analyzed with digital photography. Other measureable lesions are defined as lesions whose dimensions can be assessed by medical imaging studies (e.g. computed tomography, magnetic resonance imaging, ultrasound, etc) or functional assessments (e.g. spirometry, audiogram, oximetry, etc).

Clinical success will be further described as a graded evaluation of potential clinical responses; 1) Excellent response: $\geq 75\%$ decrease; 2) Good response: $\geq 50\%$ and $< 75\%$ reduction; 3) Moderate response: $\geq 25\%$ to $< 50\%$ reduction; 4) Minimal response: $< 25\%$ reduction; 5) No response: an increase or no reduction in the size of the lesion. Clinical responses will be determined by the principal investigator for the assessment of clinical success.

All efficacy results will be presented descriptively by individual subjects, including summarized hypoplasminogenemia symptoms over time recorded in subject diaries. The small sample size and high variability of disease presentation do not allow formal statistical analyses.

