	
The secondary PK endpoints include individual PK profiles at the end of Segment 2, compared with their PK profiles at baseline, and trough plasminogen activity and antigen levels during Segment 2 and Segment 3. Plasminogen activity and antigen levels will be presented by individual subjects and summarized descriptively (number of subjects, mean, standard deviation [SD], coefficient of variation [CV], median, minimum, maximum, geometric mean and associated CV). Individual and median profiles of the concentration-time data will be plotted using nominal times. Median profiles may be presented on both linear-linear and linear-log scales.
 
Standard PK parameters, including area under the curve (AUC), clearance (CL), mean residence time (MRT), volume of distribution (V_d) and terminal half-life ($t_{1/2}$) will be calculated using non-compartmental analysis and baseline-adjusted plasminogen activity levels derived from Segment 1 data and, if a subject is suspected to develop neutralizing antibody to the IMP, plasminogen activity levels at the end of Segment 2. Additional PK compartmental analysis may be performed and best-fit model will be used for further individual PK prediction.
 
D-dimer is monitored as a potential pharmacodynamic marker to better understand if there is a relationship between the levels of D-dimer in subjects over time and the subject's potential response to therapy.
 
Safety Analysis
 
For analysis of safety and tolerability, TEAEs and SAEs will be summarized descriptively. Clinical laboratory tests (hematology, biochemistry, urinalysis, fibrinolysis/coagulation) will be presented in summary and shift tables. The numbers of subjects who had changes from baseline in viral tests and immunogenicity tests will be presented in individual subject listings and summary tables.
 
Efficacy Analysis
 
The primary efficacy endpoint is:
 
Overall clinical success in number and size of lesions as measured by photographic or other imaging modality depending on the organ system affected or change in affected organ functionality at 48 weeks
 
The secondary efficacy endpoints are
 
• Overall clinical success in number and size of lesions as measured by photographic or other imaging modality depending on the organ system affected or change in affected organ functionality at 12 weeks• CGI scores at 12 and 48 weeks• Quality of life scores at 12 and 48 weeks
--	--

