	
Clinical success is considered achieved if 50% of subjects with visible or other measureable lesions demonstrate at least a 50% improvement in lesion number/size or functionality impact from baseline at 12 and/or 48 weeks. Visible lesions are defined as lesions which can imaged and analyzed with digital photography. Other measureable lesions are defined as lesions whose dimensions can be assessed by medical imaging studies (e.g., computed tomography, magnetic resonance imaging, ultrasound, etc.) or organ specific functional assessments (e.g., spirometry, audiogram, oximetry, etc.).
 
All efficacy results will be presented descriptively by individual subjects, including summarized hypoplasminogenemia symptoms over time recorded in subject diaries.
 
The small sample size and high variability of disease presentation do not allow formal statistical analyses.

--	--

Table of Contents

Protocol Synopsis	4
Table of Contents	14
List of In-text Tables.....	17
List of In-text Figures	17
List of Abbreviations and Definitions of Terms.....	18
1 Introduction.....	20
1.1 Background	20
1.1.1 Overview of Hypoplasminogenemia	20
1.1.2 Current Treatment for Hypoplasminogenemia	20
1.2 Pre-clinical Experience with Plasminogen.....	21
1.3 Clinical Experience with Plasminogen.....	22
1.4 Benefit Versus Risk and Study Rationale	24
1.5 Dose Rationale	25
2 Study Objectives.....	27
2.1 Primary Objectives	27
2.2 Secondary Objectives	27
3 Study Design	27
3.1 Overall Study Design	27
3.2 Treatment, Dosage, and Duration.....	30
3.2.1 Inclusion Criteria	31
3.2.2 Exclusion Criteria	32
3.3 Measures to Minimize or Avoid Bias.....	33
3.3.1 Randomization.....	33
3.3.2 Blinding	33
3.4 Study Procedures	33
3.4.1 Procedures by Visit.....	36
3.4.1.1 Screening.....	36
3.4.1.2 Baseline Assessments (Either Segment 1, Day -4 or Segment 2, Day 0) ...	36
3.4.1.3 Segment 1, Week 0, Day -4 (Participants Only)	37
3.4.1.4 Segment 1, Week 0, Day -3, Day -2, and Day -1 (Participants Only)	38

3.4.1.5	Segment 2, Week 1, Day 0.....	38
3.4.1.6	Segment 2, Week 2, Week 6, Week 10.....	38
3.4.1.7	Segment 2, Weeks 4 and 8.....	39
3.4.1.8	Segment 2, Week 12 or Discontinuation.....	39
3.4.1.9	Segment 3.....	40
3.4.1.10	End of Study Visit for US Subjects Only.....	41
3.4.1.11	Safety Follow-up Visit.....	41
3.4.2	Description of Assessments.....	42
3.4.2.1	Informed Consent/Assent.....	42
3.4.2.2	Demographics.....	42
3.4.2.3	Medical History and Disease History and Symptoms.....	42

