3.5.2.13 Clinical Assessments

All subjects will be clinically evaluated by the investigator for the clinical manifestation and severity of hypoplasminogenemia at the time points specified in the Schedule of Events table.

Measurement of Visible Lesions

The size (length and width) of visible lesions, such as ocular and gingival lesions, in subjects who have ligneous conjunctivitis will be measured and documented using photography at each visit. The procedure of photographic measurements is described in the Study Manual.

Imaging

Nonvisible lesions (ureteral, oropharyngeal, and bronchial) may be qualitatively evaluated as appropriate via imaging studies, such as computed tomography (CT) scans, X-ray, or other suitable imaging techniques at the Investigator's discretion. For example, if there is lung involvement suspected, lesions may be monitored via a CT scan obtained at Screening (unless already available within the past 6 months) and at the Week 12 visit, and at other time points if warranted.

Functionality Testing

Spirometry may be performed in subjects who have respiratory tract involvement of hypoplasminogenemia, if deemed appropriate by the investigator. The spirometry will measure forced expiratory volume in 1 second (FEV1), forced vital capacity (FVC), peak expiratory flow (PEF), and FEV1/FVC ratio. If applicable, these tests may be performed at Screening and Baseline (before the first dose of IMP), and every 4 weeks subsequently. However, no testing beyond Baseline is warranted if the subject's lung function is within normal limits at Screening and/or Baseline. Spirometry does not need to be repeated at Baseline if Screening is within 3 weeks of Baseline. Other functional tests appropriate for the affected organ system may be performed and analyzed as determined by the PI.

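### The primary efficacy response has a numeric threshold, but the unblinded investigator determines it without a stated link to the recorded measurements, and the supporting grades misfit functional measures

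*Protocol*

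**What the plan says.** The primary efficacy endpoint in Protocol section 6.3.3 is "Overall Clinical Success in number and size of lesions or change in organ functionality at 48 weeks". A subject responds with "at least a 50% improvement in lesion number/size or functionality impact from baseline", and the trial succeeds if 50% of subjects with visible or other measurable lesions do so. The synopsis gives the same rule and describes lesions "as measured by photographic or other imaging modality depending on the organ system affected".

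Section 6.3.3 includes imaged lesions on a dimensional basis: "Other measureable lesions are defined as lesions whose dimensions can be assessed by medical imaging studies". It also counts functional assessments, naming spirometry, audiogram and oximetry. Five grades then describe success further. The first four are worded as a decrease or reduction, and the last reads "No response: an increase or no reduction in the size of the lesion". The section adds: "Clinical responses will be determined by the principal investigator for the assessment of clinical success".

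On data collection, section 3.5.2.13 has visible lesions measured by length and width with photography at each visit, but says: "Nonvisible lesions (ureteral, oropharyngeal, and bronchial) may be qualitatively evaluated as appropriate via imaging studies". Table 2 schedules clinical assessments at every 12-week visit in Segment 3. Its note g lets their type and timing depend on disease presentation and leaves nonvisible imaging to the investigator. Section 3.5.1.9 makes Segment 3 clinical assessments conditional on being indicated. Sections 3.4.1 and 3.4.2 state that there is no randomization and no blinding.

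**The concern.** A percentage-change responder rule protects a single-arm, open study only if the percentage comes from recorded measurements. Here the protocol sets the threshold and then gives the response to someone who knows the treatment and the time point. It does not say that the recorded numbers decide.

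The protocol's other wording leaves room for judgement in two places. The grades do not describe improvement for measures that get better by rising. The plan also does not say what happens to a nonvisible lesion that was only looked at and never measured. For subjects with only nonvisible or functional disease, the reported response and grade could therefore depend on how one person reads the rule. At stake is the credibility of the primary response rate and its grade distribution in a pivotal study of 15 subjects.

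**Working it through.** **Inputs.** Subject threshold 50% and study threshold 50% (section 6.3.3); 15 subjects (sections 1.3 and 6.4). Section 6.4 reports no sample size calculation and section 6.3.3 no formal test, so there is no plan figure to reproduce. The number of subjects with measurable disease is not given; I assume 5, 10 or 15.

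**1. Link between measurement and response.** The synopsis speaks of measured lesions and section 6.3.3 of a 50% threshold. The sentence that assigns the response mentions neither. No independent or time-point-masked reading is described.

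**2. The grades applied literally.** Reduction = 100 × (baseline − follow-up) / baseline. The patient values are illustrations, except the 15 × 5 mm baseline, which is in section 1.3.

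| Case | Calculation | Grade |
|---|---|---|
| Lesion 15 × 5 to 7 × 5 mm | 100 × (75 − 35)/75 = 53.3% | Good, as intended |
| FEV1 1.0 to 1.6 L | 100 × (1.0 − 1.6)/1.0 = −60% | Minimal (below 25%) or No response |
| Saturation 90 to 95% | 100 × (90 − 95)/90 = −5.6% | Minimal or No response |
| The same, as deficit from 100 | 100 × (10 − 5)/10 = 50% | Good |
| No change | 0% | Both Minimal and No response |

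The last row is the overlap: zero reduction is below 25% and is also no reduction. On a scale capped at 100, a 50% gain in the raw value is impossible from any baseline above 100/1.5 = 66.7. An audiogram threshold can fall with improvement, so the misfit is clearest for spirometry and oximetry.

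**3. Nonvisible lesions.** A qualitative reading gives no percentage. Such a lesion either leaves the measurable class or is judged responsive without a number, and the text does not say which. The Week 48 visit is scheduled. Note g and section 3.5.1.9 mean that a Week 48 measurement is not secured for every such lesion.

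**4. Size.** One subject moves the rate by 100/n. Responders needed are n/2 rounded up. Starting from all responders, failure takes n − needed + 1 reversals.

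| n (assumed) | One subject | Needed | Reversals to fail |
|---|---|---|---|
| 5 | 20 points | 3 | 5 − 3 + 1 = 3 |
| 10 | 10 points | 5 | 10 − 5 + 1 = 6 |
| 15 | 6.7 points | 8 | 15 − 8 + 1 = 8 |

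Section 1.3 reports 13 of 14 visible lesions resolved at Week 12 (13/14 = 92.9%). The remaining lesion went from 15 × 5 = 75 mm² to too small to measure. By size that is close to a 100% fall, while by number it may still count as one lesion, so the two changes should be shown separately.

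**The case against.** Four points on the other side carry weight.

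- **No strict contradiction.** A reader might infer that sections 3.5.2.13 and 6.3.3 contradict each other on nonvisible lesions. They do not. The first is permissive, and the second admits only lesions with assessable dimensions or functional tests, so a purely qualitative reading can simply fall outside the measurable class. What stands is that the protocol never says so.
- **The grades are descriptive.** A reader might infer that their wording decides the primary endpoint. It does not: the 50% rule is neutral in direction and names function. The phrase about functional impact could even mean reduction of a deficit, but the text does not say that. What stands is a wording defect in a reported scale.
- **Functional disease can yield numbers.** Section 3.5.2.13 lists FEV1, FVC, PEF and their ratio, and allows testing every 4 weeks. Where done, these are recorded values. The testing is at the investigator's discretion.
- **Investigator determination need not mean unanchored judgement.** Numeric thresholds exist, the photographic procedure is in a Study Manual that is not shown, and results are presented by subject. A SAP may also define the derivation. Even so, the sentence in section 6.3.3 does not require the measurements to decide.

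A reader might also infer that over-calling could turn a failed trial into a success. With an assumed true response rate of 30%, over-calling 20% of non-responders raises the chance of declaring success from 0.15 to 0.47 (n = 10) or from 0.05 to 0.32 (n = 15). Nothing in the protocol supports a 30% rate. The Week 12 lesion result points well above it, although that result is per lesion, covers visible lesions only, and is not at Week 48.

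**Conclusion.** The concern holds in a limited form. The protocol leaves the primary response to an unblinded investigator without tying it to the recorded numbers. Its grades misgrade functional measures that improve by rising and overlap at no reduction. It also leaves the status of qualitatively read lesions open.

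Visible lesions are less exposed because their length and width are recorded. The exposure is mainly in the reported rate and grades, at 6.7 to 20 points per subject over the assumed denominators. The 50% pass or fail is probably robust. How many subjects have only nonvisible or functional disease is not stated, so the number affected cannot be given. This should be corrected, but it does not by itself put the trial's conclusion in doubt.

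**What to change.** If the SAP does not already settle these points, set them before database lock, dated and disclosed as set after all subjects had passed 48 weeks.

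1. Derive each subject's response by program from recorded baseline and Week 48 measurements, using the existing 50% threshold. List changes in lesion size and lesion number separately. Report the investigator's grade as supportive.
2. State in sections 3.5.2.13 and 6.3.3 that only lesions with recorded baseline dimensions, or an abnormal baseline functional test, enter the primary denominator. List lesions read only qualitatively as descriptive data.
3. Reword the grades as percentage improvement, with functional response defined as reduction of the deficit from normal or predicted, and make the two lowest grades exclusive.
4. Report how many Week 48 measurements are missing. Leave section 6.2 unchanged for the main rate, and show the rate with missing counted as non-response as a sensitivity analysis.

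Do not add a condition such as no rise in lesion count. That would tighten the primary criterion after the data had accrued.

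The cost is wording, a derivation program and listings, with no new visits, scans or staff. Some nonvisible lesions become descriptive only, and the rate may be slightly lower. The sensitivity rate will count as a failure any subject not rescanned because a lesion had cleared. Site measurements remain unmasked, so this limits the judgement in the response but not in the measuring.

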6.3.4 Safety Analysis

For safety analyses, treatment emergent adverse events (TEAEs) and SAEs will be summarized descriptively. Clinical laboratory tests (hematology, biochemistry, urinalysis, fibrinolysis/coagulation) will be presented in summary and shift tables. The numbers of subjects who had changes from baseline in viral tests and immunogenicity tests will be presented in individual subject listings and summary tables.

6.4 Sample Size

Approximately 15 subjects with hypoplasminogenemia will be enrolled in this study to achieve at least 10 evaluable subjects. No formal calculation was made for sample size because of the rarity of the disease. The sample size is based on known patients who have hypoplasminogenemia.

6.5 Interim Analysis

The data in this study will be conducted in stages. An initial analysis of the PK data will be conducted when at least 10 subjects have completed Segment 2 dosing and have provided sufficient samples for PK assessments. The second data analysis will be conducted when all subjects have either completed the Week 48 visit or have withdrawn consent and completed the final safety visit. The final data analysis will occur when all subjects have completed the final safety visit or remain in the study in Segment 3 (US subjects only). Additional details for these analyses will be included in the Statistical Analysis Plan (SAP).

7 Management of Investigational Medicinal Product

7.1 Packaging and Labeling in the US

The IMP for IV administration is in a lyophilized presentation and will be available in 50 mL vial size. Each vial contains 62.5 mg Plasminogen, which will yield a concentration of 5 mg/mL after it is reconstituted in 12.5 mL of Water for Injection. The IMP is labeled as below:

Protocol #: 2002C011G 50 mL

Plasminogen Human

LOT NO: 2388 - XXX

Caution: New Drug-Limited by Federal (US) Law to
Investigational Use – For Clinical Trial Use Only

Mfg Date: XXXXXXXX Store at $\leq 2^{\circ}\text{C}$ to 8°C

Manufactured by ProMetic BioProduction Inc, Laval, Quebec, H7V 1B7 and

Emergent BioSolutions Inc, Baltimore, MD, 21230

For ProMetic BioTherapeutics Inc., Rockville, MD, 20850

There will be a separate IMP manual for Norway which will include the label with expiry date.

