Indication	Systemic treatment of Type I plasminogen deficiency (hypoplasminogenemia)
Phase	2/3 (pivotal)
Investigational Medicinal Product	Plasminogen (Human) Intravenous (IV), lyophilized material reconstituted with Water for Injection to produce a sterile suspension with a concentration of 5.5 mg/mL
Objectives	
Primary objectives:
 
• To achieve an increase of individual trough plasminogen activity by at least an absolute 10% (i.e., 10 U/dL) from baseline in adult and pediatric subjects with hypoplasminogenemia during the 12 weeks of plasminogen replacement therapy in Segment 2;• To evaluate the efficacy of plasminogen replacement therapy on clinically evident or visible lesions of hypoplasminogenemia during 48 weeks of dosing in Segments 2 and 3. 
Secondary objectives:
 
• To evaluate the safety and tolerability of plasminogen replacement therapy during the 48 weeks of dosing;• To evaluate the efficacy of plasminogen replacement therapy on clinically evident or visible symptoms of hypoplasminogenemia during the 12 weeks of dosing in Segment 2.• To evaluate the effect of plasminogen replacement therapy on pharmacokinetics and immunogenicity during the 48 weeks of dosing.
Study Sites	This study will be conducted in at least 2 sites, including at least 1 site in the US and 1 in Norway.
Study Design	Approximately 15 subjects aged 2 to 80 years with hypoplasminogenemia will be enrolled to ensure a sample size of at least 10 PK-evaluable subjects. At least 2 pediatric subjects, aged 2 to 18 years, will be enrolled. An evaluable subject for PK is defined as a subject who completes Segment 2

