
Duration
	
For each subject, the estimated duration of study participation is no more than 21 days for screening, 4 days for Segment 1, 12 weeks for Segment 2, and 40 weeks (36 weeks Treatment and 4 weeks Safety Follow-up) for subjects who participate in Segment 3 in Norway.
 
For those subjects who participate in Segment 3 in the United States, it will be dependent on product approval and sponsor decision. A Safety Follow-up visit is required 30 days after the final IMP dose. However, due to the delay in product approval, subjects at the US site will be allowed to enroll in Treatment Protocol 2002C018G and continue ongoing IMP treatment without any break in treatment. If subjects decide to enter Treatment Protocol 2002C018G, then they will return to the study site and complete the End of Study visit and sign an informed consent/assent for that study and stop participation in the current study. If subjects decide to not enter Treatment Protocol 2002C018G, then they will stop IMP and return to the study site for a Safety Follow-up visit 30 days after the final IMP dose.

Administration & Dosage	
IMP Preparation
 
Plasminogen (Human) Intravenous lyophilized material will be reconstituted with sterile Water for Injection to yield a solution of 5.5 mg/mL for IV infusion.
 
Infusion
 
Only eligible and enrolled subjects will receive IMP. The entire dose of the Plasminogen IV solution should be calculated on the basis of each subject's body weight and infused over 10 to 30 minutes.
 
Dose and Dosing Interval
 
In Segment 1, a single dose of 6.6 mg/kg Plasminogen will be administered to each subject. However, subjects who have documented individual PK profiles with the sponsor (e.g., due to participation in the previous Phase 1 study and received 6.6 mg/kg Plasminogen) do not need to undergo Segment 1 and can proceed directly to Segment 2.
 
In Segment 2, repeated doses of 6.6 mg/kg Plasminogen will be administered every second, third, or fourth day, depending on individual PK profile. Subjects will receive a range of 21 to 42 doses in Segment 2.
 
The dosage and dosing interval in Segment 3 will be the same as Segment 2, with the possibility of modification based on discussion between the Investigator and the sponsor.

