In the current study, an interim analysis was performed after the first 10 subjects completed 12 weeks of treatment with a data cutoff at 30 November 2016. All 10 of these subjects achieved target PK trough levels demonstrating the ability of Prometic's Plasminogen (Human) to serve as effective replacement therapy. Preliminary efficacy evaluation at 12 weeks revealed that 13 of 14 visible lesions had resolved, and the remaining lesion had improved from 15 × 5 mm at baseline to too small to be measured at 12 weeks. There were no recurrences and no new lesions during this period of observation. There were no deaths, serious adverse events (SAEs), or AEs resulting in discontinuation of study drug. The most frequent AEs were headache and nasopharyngitis. Nausea, diarrhea, rhinorrhea, sinusitis, epistaxis, back pain, pain in extremity, and hematuria were also frequent in adult subjects, and upper abdominal pain and cough were frequent AEs in pediatric subjects. A US Biologics Licensing Application was submitted based on these interim data; this application is under review. As of 14Dec2017 study enrollment is complete and all 15 enrolled subjects received at least 48 weeks of treatment. Three subjects in Norway completed the study as planned, with the remaining 12 subjects in the US continuing treatment until product licensing or study termination by the Sponsor. However, due to the delay in product approval, subjects at the US site will be allowed to enroll in Treatment Protocol 2002C018G and continue ongoing IMP treatment without any break in treatment. If subjects decide to enter Treatment Protocol 2002C018G, then they will return to the study site and complete the End of Study visit and sign an informed consent/assent for that study and stop participation in the current study. If subjects decide to not enter Treatment Protocol 2002C018G,

then they will stop IMP and return to the study site for a Safety Follow-up visit 30 days after the final IMP dose.

Subject dosing has been revised throughout the protocol from 6.0 mg/kg to 6.6 mg/kg of plasminogen to reflect the true concentration and dosing as agreed with FDA during the 05Oct2016 Pre-BLA Meeting (CRMTS# 10393).

Details of these studies can be found in the Investigator's Brochure (IB).

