7.5 Preparation

IMP infusions should be prepared by a pharmacist or a qualified designee (subjects will be trained by site personnel for home preparation and infusion).

IMP must be removed from refrigerated storage and brought to room temperature for reconstitution with 12.5 mL of Water for Injection using sterile technique. The IMP should be reconstituted by addition of water slowly with swirling until dissolved. After reconstitution, the plasminogen solution should be colorless and clear to slightly opalescent. Reconstituted plasminogen must be used within 3 hours after reconstitution.

Please see the Pharmacy Manual for complete details regarding drug reconstitution.

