7.6 Administration

Only eligible and enrolled subjects will receive IMP. The entire dose of the Plasminogen IV solution should be calculated on the basis of each subject's body weight and infused over a period of 10 to 30 minutes. IMP will be administered using a syringe with filter or disk filter according to the instructions in the Pharmacy Manual.

8 Records Management

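### Section 7.1 gives a product strength of 5 mg/mL where the synopsis gives 5.5 mg/mL; paired with the 6.6 mg/kg dose, the section 7.1 figure yields an infusion volume 10% too large

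*Protocol*

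**What the plan says.** The protocol gives two strengths for one product.

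- **Synopsis, Investigational Medicinal Product:** the lyophilized material is "reconstituted with Water for Injection to produce a sterile suspension with a concentration of 5.5 mg/mL".
- **Synopsis, Administration & Dosage:** the material "will be reconstituted with sterile Water for Injection to yield a solution of 5.5 mg/mL for IV infusion". The 6.6 mg/kg dose appears in the same block.
- **Section 7.1:** "Each vial contains 62.5 mg Plasminogen, which will yield a concentration of 5 mg/mL after it is reconstituted in 12.5 mL". The label text reproduced there shows no strength.
- **Section 7.5:** the vial is "brought to room temperature for reconstitution with 12.5 mL of Water for Injection using sterile technique", the same diluent volume as in section 7.1.
- **Section 7.6:** "The entire dose of the Plasminogen IV solution should be calculated on the basis of" body weight. No mL/kg figure follows.

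Section 1.3 gives the history: "Subject dosing has been revised throughout the protocol from 6.0 mg/kg to 6.6 mg/kg of plasminogen to reflect the true concentration and dosing". By that account, the FDA accepted the change in October 2016.

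**The concern.** Every infusion in this study is weight-based, so the volume drawn up depends on two numbers, the dose per kilogram and the strength of the solution. The dose was revised and section 7.1 still carries a strength that matches the old dose. Someone who takes the current dose from section 3.2 and looks in section 7, the product-management section, for the strength will find only 5 mg/mL.

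Section 7.1 is the US packaging section. Section 1.3 reports three Norwegian subjects as having completed, "with the remaining 12 subjects in the US continuing treatment until product licensing or study termination by the Sponsor". Section 7.5 adds that "subjects will be trained by site personnel for home preparation and infusion". What is at stake is a 10% overstatement of the infused volume if the two mismatched figures are combined. The trough-level and lesion endpoints are not at issue.

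**Working it through.** **Inputs**

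| Quantity | Value | Source |
|---|---|---|
| Vial content | 62.5 mg | Section 7.1 |
| Diluent volume | 12.5 mL | Sections 7.1 and 7.5 |
| Strength, section 7 | 5 mg/mL | Section 7.1 |
| Strength, synopsis | 5.5 mg/mL | Synopsis, two places |
| Former dose | 6.0 mg/kg | Section 1.3 |
| Current dose | 6.6 mg/kg | Sections 1.3 and 3.2, synopsis |

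**Step 1. Reproduce the section 7.1 figure.** Strength = content / volume = 62.5 / 12.5 = 5.0 mg/mL. Section 7.1 is consistent within itself. It therefore looks like an older, coherent pair of numbers and not a typing slip.

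**Step 2. Which strength is current?** The dose changed by 6.6 / 6.0 = 1.10. The two strengths differ by 5.5 / 5.0 = 1.10. Volume per kilogram = dose / strength:

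- old pair: 6.0 / 5.0 = 1.20 mL/kg
- new pair: 6.6 / 5.5 = 1.20 mL/kg

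The infused volume is unchanged if both figures move together. That fits the reason given in section 1.3, a restatement of the same infusion at its true concentration.

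**Step 3. Vial content implied by 5.5 mg/mL.** Taking the final volume as the 12.5 mL of diluent, 5.5 × 12.5 = 68.75 mg, against 62.5 mg stated.

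**Step 4. The mixed pair.** The current dose with the section 7.1 strength gives 6.6 / 5.0 = 1.32 mL/kg. Relative to the intended volume, 1.32 / 1.20 = 1.10, or +10%. If the solution is in fact 5.5 mg/mL, the dose delivered is 1.32 × 5.5 = 7.26 mg/kg instead of 6.6.

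**Step 5. Illustration at assumed body weights, contents at 5.5 mg/mL**

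| Weight (assumed) | Volume at 1.20 mL/kg | Volume at 1.32 mL/kg | Dose at 1.20 mL/kg | Dose at 1.32 mL/kg |
|---|---|---|---|---|
| 20 kg | 24.0 mL | 26.4 mL | 132.0 mg | 145.2 mg |
| 70 kg | 84.0 mL | 92.4 mL | 462.0 mg | 508.2 mg |

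**Step 6. The opposite case.** If 5 mg/mL were the true strength and the synopsis were wrong, a volume of 1.20 mL/kg would deliver 1.20 × 5.0 = 6.0 mg/kg, and 6.0 / 6.6 = 0.909, about 9% below the stated dose. One of the two statements has to change whichever strength is right.

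**The case against.** The strongest reply is that section 7.1 describes packaging and is not a preparation instruction. Section 7.5 sends preparers to the Pharmacy Manual for full reconstitution details, section 7.6 refers to it for administration, and section 7.4 says it will carry the instructions for subjects who prepare doses at home. Those subjects are also trained by site staff. A reader who looks up the dose in the synopsis finds the correct strength beside it. Enrolment was complete, all 15 subjects had at least 48 weeks of treatment, and the remaining US subjects were to move to another treatment protocol or stop, so few volumes were likely to be worked out afresh from section 7.1. Nor is 7.26 mg/kg shown to cross any safety limit. Section 3.2 lets the investigator shorten the Segment 3 interval, and going from every third to every second day raises the dose rate by half (3/2 = 1.5).

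Much of this stands. It limits the likely consequence and rules out any claim that subjects were overdosed. It is also fair that the protocol never calls 5 mg/mL superseded, that 68.75 mg assumes a final volume of exactly 12.5 mL, and that the problem is an inconsistency between sections, since the division in section 7.1 is correct. None of it reconciles the two strengths. A manual that is not shown may hold the right figure, but that does not make the protocol's figure right, and the manual should be checked against a protocol that is itself correct.

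**Conclusion.** The point holds, and the figure should be fixed. The current protocol text states two strengths for the same product, and nothing in the text available resolves them. That 5.5 mg/mL is the current value is an inference, but a strong one: it rests on the stated reason for the dose revision and on the exact match of the two 1.10 ratios. On that basis section 7.1 is wrong as written. Combining it with the current dose gives 1.32 instead of 1.20 mL/kg, a 10% excess. The excess arises only if someone derives the volume from section 7.1. Actual misdosing is not established, and no effect on any endpoint is claimed. Confidence is high on the contradiction and lower on the exact replacement vial content.

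**What to change.** 1. In section 7.1, change the strength to 5.5 mg/mL and give the matching vial content (68.75 mg at 12.5 mL, subject to the sponsor's confirmation of content and final volume).
2. State the infusion volume once, 1.20 mL/kg, in section 7.5 or 7.6, so that nobody has to derive it.
3. Check that the Pharmacy Manual, the home-infusion instructions and the separate Norway product manual use the same strength and volume.
4. In the same edit, settle on one label for the Phase 1 dose whose profile lets a subject skip Segment 1. It reads 6 mg/kg in the synopsis study design, sections 3.1, 3.2, 3.5.1.3 and 3.5.2.6 and Table 2 footnote a, but 6.6 mg/kg in the synopsis blocks on dosage and on criteria of evaluation. This is editorial and does not affect the infused volume.

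The cost is one corrected sentence, one added statement, some label edits and a document cross-check. No additional data are needed.
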